12.1.8. Yale-Brown Obsessive-Compulsive Scale-II (Y-BOCS-II)³⁰

The Y-BOCS-II is a 10-item clinician-rated measure of OCD symptom severity. Raters assess obsessions and compulsions separately in five domains: time spent, interference, distress, resistance, and control. Each domain is rated on a scale from 0 to 4. Total scores range from 0 to 40, with higher scores indicating greater symptom severity.

The lookback period for each item is dichotomously rated. Administration time is approximately 10 minutes.

12.1.9. Swanson, Nolan and Pelham SNAP-IV-26)¹³

The SNAP-IV-26 questionnaire is designed to assess ADHD core symptoms of inattention (items 1-9), hyperactivity/impulsivity (items 10 18), and symptoms of oppositional defiant disorder (ODD) (items 19-26) in children and adolescents 6-18 years of age. In this study, 18-year-olds are defined as adults and will complete the CAARS-S:S adult scale.

All 26 items are rated on 4-point scale and the total score ranges from 0-78, with higher scores indicating greater severity.

It is rated by the caregiver(s) as present or absent at the time of evaluation on a 0-3-point scale. Completion time is approximately 10 minutes.

12.1.10. Conners Adult ADHD Rating Scale – Self Report, Short Version (CAARS-S:S)

The CAARS³¹ is a 26-item self-report questionnaire assessing ADHD symptoms in adults (ages 18 and older). Subjects are asked to rate themselves on a range of symptoms and behaviors associated with ADHD in adults, using a 4-point scale and the total score ranges from 0-78 with higher scores indicating greater severity.

It is rated by the subject as present or absent at the time of evaluation on a 0-3-point scale. Completion time is approximately 5 minutes.

Emalex Biosciences, Inc.

Protocol EBS-101-TD-301
Ecopipam

Version 9.0, 05 March 2024

12.1.11. Vital Signs

Vital signs [blood pressure (after being supine for 5 minutes), pulse, height (children and adolescents only) and weight] will be collected at each clinic visit per Table 3.

12.1.12. Electrocardiogram (ECG)

Sites will be provided with a 12-lead ECG device to complete assessments per Table 3. Clinicians will instruct subjects to follow-up with care as appropriate upon evidence of new or worsening abnormal ECG readings.

12.1.13. Central Laboratory Tests:

Subjects should be in fasting state (minimum of 8 hours) for all blood laboratory tests collected at study visits after the Screening visit, per Table 3.

| Category | Test names |
|-------------------|--|
| Hematology | Red blood cell (RBC) count, hemoglobin (Hb), hematocrit (Hct), platelets, and white blood cell (WBC) count with differential (neutrophils, bands lymphocytes, monocytes, eosinophils, basophils, immature granulocyte) Mean Corpuscular Hemoglobin (MCH), Mean Corpuscular Hemoglobin Concentration (MCHC), Mean Corpuscular Volume (MCV), Mean Platelet Volume (MPV), Red Cell Distribution Width (RDW), CBC, Nucleated Red Blood Cell |
| Chemistry | Glucose, calcium, albumin, cholesterol, triglycerides, phosphorus, lactate dehydrogenase (LDH), total protein, globulin, prolactin; Liver function tests: albumin, alkaline phosphatase (ALP), aspartate aminotransferase (AST/SGOT), alanine aminotransferase (ALT/SGPT), total bilirubin, direct bilirubin, Calcium (Ca), Total cholest rol, glucose, lactate dehydrogenase (LDH), phosphorous, total protein, triglycerides; Electrolytes: sodium (Na), potassium (K), chloride (Cl), bicarbonate; Renal function tests: Blood urea/blood urea nitrogen (BUN), creatinine |
| Urinalysis | Complete urinalysis includes color, appearance, specific gravity, pH, protein, glucose, ketones, and blood with microscopic examination for positive protein or blood results |
| Pregnancy Test | A local urine test (for women of childbearing potential only) and central laboratory serum test to confirm a positive urine result |
| Urine Drug Screen | Central laboratory test to detect the presence of cocaine, amphetamine, benzodiazepines, barbiturates, phencyclidine (PCP), opiates |
| Special Test | Hemoglobin A1c (HbA1c) at Baseline, Week 12 and Week 24 |

| Emalex Biosciences, Inc. | Protocol EBS-101-TD-301 |
|--------------------------|----------------------------|
| Ecopipam | Version 9.0, 05 March 2024 |

Maximum blood volume to be drawn at each visit is noted below.

| Visit | Maximum Blood Volume (mL) |
|-----------------------------|---------------------------|
| Visit 1 – Screening | 6 |
| Visit 2 – Baseline | 8 |
| Visit 3 – Week 4 | 14 |
| Visit 4 – Week 8 | 6 |
| Visit 5 – Week 12 | 12 |
| Visit 10 – Week 18 | 6 |
| Visit 13 – Week 24/Relapse/ | ET 8 |
| Visit 14 – 7 Day Follow Up | 6 |
| Visit 15 – 14 Day Follow Up | 6 |

Total volume at each visit does not exceed 1% of the total blood volume and the total volume of all blood samples does not exceed 3% of the total blood volume.

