During the R/WD period, subjects will return to the clinic every week for the first 4 weeks and every 2 weeks thereafter (Weeks 13, 14, 15, 16, 18, 20, 22 and 24) and efficacy and safety assessments will be conducted at each of these visits.

Any subject meeting Relapse criteria, defined as loss of $\geq 50\%$ of the improvement experienced on the YGTSS-TTS from Baseline (Day 1) to the last visit of the open-label Stabilization period (Week 12), or initiation of additional medications to treat symptoms of TD, or requirement of hospitalization for worsening symptoms of TD will be withdrawn from blinded study medication (ecopipam or placebo).

Non-responders to ecopipam during the open-label Stabilization period at either Week 8 or Week 12, or Responders randomized to ecopipam who complete the R/WD period, or who meet

Relapse criteria during the R/WD period, or who discontinue the study prematurely for any reason will be tapered off ecopipam in decrements of 22.4 mg/day (25 mg/day ecopipam HCl) and will complete the Week 24/Relapse/ET visit. Subjects assigned to placebo will receive placebo taper down medication to preserve the blind.

Follow Up visits will be conducted in the clinic 7 and 14 days after the last dose of study medication followed by a telephone call 30 days after the last dose of study medication to determine any adverse events, with the exception of subjects who roll into the open-label extension study EBS-101-TD-391within 30 days of their last study drug.

Subjects who experience Relapse may be treated for their TD with medications recommended by the PI or referred back to their primary physician for treatment after completing Day 7 and 14 follow-up visits.

[figure not shown]
Responders to ecopipam who complete the R/WD period and who complete the Week 24/Relapse/ET visit and the Day 7 and 14 follow-up visits are eligible to enter the long-term open-label study EBS-101-TD-391. Subjects who meet the criteria for Relapse and complete the Week 24/Relapse/ET visit and the Day 7 and 14 follow-up visits will have the opportunity to enter the long-term open-label study..

In anticipation of reaching the target number of Relapse events, randomization into the double-blind R/WD period may be closed, at which time subjects in the open-label Stabilization period may continue in the study until the Week 12 visit Upon completion of the Week 12 visit, subjects will have the opportunity to enter the long-term open-label study, EBS-101-TD-391.

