7.5. Criteria for Subject Study Discontinuation

A subject may elect to discontinue from the study at any time for safety or personal reasons. All subjects who discontinue from the study should complete the early termination procedures.

Any subject with a new positive response on questions 4 and/or 5 of the Columbia Suicide Severity Rating Scale (C-SSRS) will be immediately discontinued and evaluated for risk.

Any subject with a CDRS-R or PHQ-9 assessment indicative of the onset of a new depressive episode at any visit can be discontinued from study participation at the discretion of the

Protocol EBS-101-TD-301 Version 9.0, 05 March 2024

Investigator. The Investigator will perform suicide risk assessment in subjects who respond positively to PHQ-9 question 9.

Subjects will be discontinued due to attempted suicide or suicidal behavior, oculogyric crisis, neuroleptic malignant syndrome, new onset seizures, serotonergic syndrome, or tardive dyskinesia. Subjects will also be discontinued if there are any adverse events that are Grade 4 (life-threatening consequences; urgent intervention indicated) in severity per CTCAE version 5.

Subjects who discontinue early from the study will be evaluated for one of these primary reasons: AE(s), lost to follow-up, subject choice, inadequate therapeutic effect, loss of efficacy, and administrative/other. In addition to the primary reason, the subject may have indicated one or more of these reasons as secondary reasons for discontinuation. Study disposition information will be collected on the CRF.

Subjects who discontinue treatment for any reason, other than an SAE (even if the SAE is not treatment related) or an AE (unless the AE can be determined to be unrelated to treatment), may be replaced only after consultation with Sponsor or its designee

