| | Screening Period ^a | Titrati | on Phase | W | Maintenance Phase Weeks 4 to 12 (Day 29 up to 84) | | | Double-Blind Randomized Withdrawal Period Weeks 12 to 24 (Days 85 to 169) | | | | | | | Safety Follow-Up (Days 170-199) | | |
| Visit/TC Study Day | Screening VISIT 1 Day -28 to -1 | Baseline VISIT 2 Day 1 | W 2 f Day 15 Telephone call only (±3d) | W4 / VISIT 3/ Day 29 (±3d) | W8 / VISIT 4 / Day 57 (±3d) | W 12 VISIT 5 Day 85 (±3d) | W13 / VISIT 6 / Day 92 (±3d) | W14 / VISIT 7 / Day 99 (±3d) | W15 / VISIT 8 / Day 106 (±3d) | W16 / VISIT 9 / Day 113 (±3d) | W18 / VISIT 10 / Day 127 (±3d) | W20 / VISIT 11 / Day 141 (±3d) | W22 / VISIT 12/ Day 155 (±3d) | W 24 VISIT 13 Day 169 or Relapse or ET (±3d) | 7 Day F/U VISIT 14 (±3d) | 14 Day F/U VISIT 15 (±3d) | 30 Day F/U ^f Telephone call only (±3d) |
| Dispense Study Drug | | X | | X^d | X | X | | | | X | | X | | X | | | |
| Collect Unused Study Drug/Assess Drug Compliance | | | | X | X | X | X | X | х | x | X | X | X | X | X | | |

Abbreviations: ADHD = attention-deficit hyperactivity disorder; AE = adverse event; BP = blood pressure; DSM-5-TR = Diagnostic and Statistical Manual of Mental Disorders, Fifth Edition; ECG = electrocardiogram; F/U = follow up; HR = heart rate; PK = pharmacokinetic(s); TD = Tourette's Disorder

Neurological exam should be part of the physical exam. Physical exam t Week 4 visit will include assessment for serotonin syndrome. If serotonin syndrome symptoms are present, local laboratory assessment should be performed.

Confidential

^a Informed consent must be obtained prior to any screening procedures. All screening procedures are to occur after confirmation of appropriate timeframe since discontinuation of applicable medications. Rescreening is allowed after approval by the Medical Advisor.

^b Vital signs will include pulse, BP (done 5 minutes after being supine) height and weight.

^c Subjects should be in a fasting state (8 hours) for laboratory t sts. Fas ing at the Screening visit is optional. HbA1c will be measured only at Baseline, Week 12, and Week 24 (completed subjects only).

d At Week 4, ecopipam should be administered after the pre-dose blood draw. PK samples will be collected at 1) pre-dose; 2), post-dose between 0.5 and 1.5 hours; and 3) post-dose between 2 and 4 hours. Week 12 PK assessment only to be performed if Week 8 assessment is missed.

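### The protocol says all blood samples stay within 3% of total blood volume, but its own listed maxima reach 66–68 mL for a randomized completer, which is above 3% throughout the 18–23 kg weight band.

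*Protocol*

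**What the plan says.** Protocol Section 12.1.13 (Central Laboratory Tests) introduces its volume table with "Maximum blood volume to be drawn at each visit is noted below". The table has nine rows, from "Visit 1 – Screening | 6" through "Visit 5 – Week 12 | 12" to the two follow-up visits. Below it stand two limits. The first caps any single visit at 1% of the subject's blood volume. The second is cumulative and reads: "the total volume of all blood samples does not exceed 3% of the total blood volume". The second limit carries no time period, and neither is restricted by weight or age.

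Four other provisions decide which draws add up for one child:

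- Inclusion criterion 3 (Section 8.1) admits subjects from 18 kg, and the lowest dosing and randomization band is 18 to 23 kg.
- Table 3 schedules PK but no central laboratory tests at Week 8. Its footnote d adds: "Week 12 PK assessment only to be performed if Week 8 assessment is missed".
- Section 7.5 says that "subjects who discontinue from the study should complete the early termination procedures".
- Section 7.1 says that "Follow Up visits will be conducted in the clinic 7 and 14 days after the last dose of study medication", and it makes both of these visits a condition of entering the extension study.

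Neither document gives a blood volume per kilogram or a total volume for the study.

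**The concern.** The 3% sentence stands directly under the table that should support it, so the two can be compared. The maxima sum to an amount that looks too large for a child near the minimum weight. Because the sentence speaks of all samples and names no period, it has to be read as a whole-study limit.

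The 3% sentence is a safety statement on blood loss, and it applies to children as light as 18 kg. Sites and ethics committees may rely on it. If it is false at the listed maxima, those who approved the sampling schedule relied on a limit that the schedule does not keep. No efficacy result depends on it.

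**Working it through.** **Inputs** (Section 12.1.13 for volumes; Table 3 and its footnotes for content)

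| Visit | Maximum, mL | Blood drawn for |
|---|---|---|
| Screening | 6 | laboratory tests |
| Baseline | 8 | laboratory tests, HbA1c |
| Week 4 | 14 | three PK samples |
| Week 8 | 6 | PK only |
| Week 12 | 12 | laboratory tests, HbA1c, PK if Week 8 PK was missed |
| Week 18 | 6 | laboratory tests |
| Week 24/Relapse/ET | 8 | laboratory tests, HbA1c (completers) |
| 7-day follow-up | 6 | laboratory tests |
| 14-day follow-up | 6 | laboratory tests |

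The plan's 3% cannot be reproduced, because no total and no mL/kg are given. The check is therefore what blood volume would make it true.

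**Totals**

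- Plain sum: 6 + 8 + 14 + 6 + 12 + 6 + 8 + 6 + 6 = 72 mL.
- Completer, Week 8 PK missed: 72 − 6 = 66 mL. Missing the PK draw does not mean missing the visit, so the child can still be a responder and be randomized.
- Completer, Week 8 PK done and Week 12 taken as 8 mL, as at Baseline (inferred): 72 − 4 = 68 mL.

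**Blood volume needed, without any outside figure**

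- 66 / 0.03 = 2,200 mL.
- At 18 kg: 2,200 / 18 = 122.2 mL/kg. At 23 kg: 2,200 / 23 = 95.7 mL/kg.

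The statement therefore fails throughout the band for any value below 95.7 mL/kg.

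**Percentages, assuming 65–85 mL/kg**

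Share = volume / (mL/kg × weight). Blood volume is 1,170–1,530 mL at 18 kg and 1,495–1,955 mL at 23 kg.

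| Path | Volume, mL | At 18 kg | At 23 kg |
|---|---|---|---|
| Completer, Week 8 PK missed | 66 | 4.31%–5.64% | 3.38%–4.41% |
| Completer, Week 8 PK done | 68 | 4.44%–5.81% | 3.48%–4.55% |
| Week 8 non-responder | 54 | 3.53%–4.62% | 2.76%–3.61% |
| Withdrawal between Weeks 4 and 8 | 48 | 3.14%–4.10% | 2.46%–3.21% |

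The last two rows are 6 + 8 + 14 + 6 + 8 + 6 + 6 = 54 and 6 + 8 + 14 + 8 + 6 + 6 = 48. At 18 kg they need 54 / 0.03 / 18 = 100.0 and 48 / 0.03 / 18 = 88.9 mL/kg. They exceed 3% at 18 kg under the assumption, but not across the whole band.

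**Where the limit becomes true.** 66 mL meets 3% from 2,200 / 85 = 25.9 kg or 2,200 / 65 = 33.8 kg, so the excess reaches into the next weight band.

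**The 1% limit per visit.** Week 4 is 14 mL, or 0.92%–1.20% at 18 kg. It meets 1% only from 14 / 0.01 / 18 = 77.8 mL/kg, so the assumption leaves this limit undetermined.

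**Would a 4-week window rescue the sentence?** The two heaviest clusters identified, at 18 kg:

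- Week 4, ET and both follow-ups: 14 + 8 + 12 = 34 mL, or 2.22%–2.91%. This exceeds 3% only below 34 / 0.03 / 18 = 63.0 mL/kg.
- Week 12 with PK, relapse at Week 13 and both follow-ups: 12 + 8 + 12 = 32 mL, or 2.09%–2.74%.

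**The case against.** The strongest reply is that the table gives ceilings, and that the 1% and 3% sentences are further limits that bind on top of them. A light child would then simply be drawn less, and actual volumes depend on a laboratory manual that is not available here. It is true that sites may draw less. But the sentence describes what the schedule does; it does not tell sites to reduce draws by weight, and no other instruction found in the protocol does so.

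A second reply is that 3% was meant per period of about four weeks. That may be so, but the text says nothing of it. Nor is the four-week reading fully secured. Late Screening (6), Baseline (8), Week 4 at Day 26 (14) and an immediate ET (8) make 36 mL, which is 3.08% at 18 kg and 65 mL/kg. That timing is very unlikely, because Eligibility Review comes between Screening and Baseline, and it breaks 3% only below 36 / 0.03 / 18 = 66.7 mL/kg.

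Three smaller points have some weight:

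- The 68 mL figure implies a 4 mL PK draw at Week 12, although the PK-only Week 8 visit is listed at 6 mL. With a 6 mL PK draw both completer totals are 66 mL, and the conclusion is the same.
- Table 3 footnote c limits Week 24 HbA1c to completed subjects, while Section 12.1 also includes early terminations. If ET is really 6 mL, the shorter paths fall to 52 and 46 mL. At 18 kg and 85 mL/kg, 46 mL is 46 / 1,530 = 3.01%, essentially at the limit. The shorter paths are therefore secondary evidence.
- The draws are spread over more than six months, and no harm is shown.

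None of this alters the completer result.

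**Conclusion.** The concern holds. At the listed maxima a randomized completer gives 66–68 mL, and the 3% sentence is untrue for such a child anywhere in the 18–23 kg band. The excess is 4.3%–5.8% at 18 kg and 3.4%–4.5% at 23 kg against the stated 3%.

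The percentages rest on an assumed 65–85 mL/kg. The conclusion is less sensitive than that: 66 mL exceeds 3% throughout the band for any blood volume below about 96 mL/kg. It does not depend on the inferred 68 mL or on the shorter paths. It concerns the ceilings and not volumes actually drawn, and no breach of the 1% per-visit limit is shown. The sentence should be corrected because it is a stated safety limit that the schedule does not guarantee for the lightest children enrolled.

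**What to change.** Make the 3% sentence true at 18 kg in one of two ways.

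- **(a) State the period.** Say what period the 3% covers, and give the true whole-study percentage at 18 kg beside the table. Four weeks appears to fit, but the sponsor should confirm it against the visit windows and name the mL/kg value used. Cost: a sentence and a figure in the protocol.
- **(b) Keep 3% for the whole study.** Set lower maxima for the lowest weight bands. At 18 kg, 3% is 35.1–45.9 mL under the same assumption, so the total has to fall by between 66 − 45.9 = 20.1 mL and 68 − 35.1 = 32.9 mL. Because the excess can extend to about 34 kg, the 23–34 kg band needs the same check. Cost: a weight-banded volume table and a laboratory-manual change.

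Option (a) is the smaller change. The choice belongs to the sponsor and the ethics committees. Neither option affects an endpoint.

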12.2. Adverse and Serious Adverse Events

12.2.1. Definition of Adverse Event

An adverse event (AE) is defined as any untoward medical occurrence in a subject administered a study drug and which does not necessarily have a causal relationship with this treatment. An AE can therefore be any unfavorable and unintended sign (including an abnormal laboratory finding), symptom, or diseas temporally associated with the use of a study drug, whether related to the study drug or not.

An abnormality identified during a medical test (e.g., laboratory parameter, vital sign, ECG data, physical exam) should be defined as an AE only if the abnormality meets one of the following criteria:

- Induces clinical signs or symptoms
- Requires active intervention
- Requires interruption or discontinuation of study medication
- The abnormality or investigational value is clinically significant in the opinion of the investigator.

12.2.1.1. Adverse Event (AE)

An AE is the development of an undesirable medical condition or the deterioration of a preexisting medical condition including worsening of TD following or during exposure to a pharmaceutical product, whether or not considered casually related to the product. In clinical

| Emalex Biosciences, Inc. | |
|--------------------------|--|
| Ecopipam | |

Protocol EBS-101-TD-301 Version 9.0, 05 March 2024

studies, an AE can include an undesirable medical condition occurring at any time, including baseline or washout periods, even if no study treatment has been administered.

All AEs that occur after any subject has been screened, enrolled, before treatment, during treatment, or within 30 days following the cessation of treatment, whether they are related to the study or not, must be recorded on forms provided by Sponsor or its representatives.

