Follow Up visits will be conducted in the clinic 7 and 14 days after the last dose of study medication. Subjects who do not roll into the open-label ext nsion study EBS-101-TD-391 will also be contacted by telephone 30 days after the last dose of s udy medication to determine any adverse events.

Subjects who experience relapse may be treated for their TD with medications recommended by the PI or referred back to their primary physician for treatment after completing Day 7 and 14 follow-up visits.

Responders to ecopipam who complete the R/WD period and who complete the Week 24/Relapse/ET visit and the Day 7 and 14 follow-up visits are eligible to enter the long-term open-label study EBS-101-TD-391. Subjects who meet he criteria for Relapse and complete the Week 24/Relapse/ET visit and the Day 7 and 14 follow-up visits will have the opportunity to enter the long-term open-label study.

In anticipation of reaching the target number of Relapse events, randomization into the double-blind R/WD period may be closed, at which time subjects in the open-label Stabilization period may continue in the study until the Week 12 visit. Upon completion of the Week 12 visit, subjects will have the opportunity to enter the long-term open-label study, EBS-101-TD-391.

The Sponsor may elect to re-open randomization as required.

Once the target number of Relapse events is met, all subjects may enter the long-term open-label study EBS-101-TD-391 once the Week 24/Relapse/ET visit and the Day 7 and 14 follow-up visits have been completed.

The study will be considered completed once all subjects have completed the 30-Day telephone Follow Up call or enter the open-label study EBS-101-TD-391.

Protocol EBS-101-TD-301 Version 9.0, 05 March 2024

Number of subjects (planned): The minimum number of subjects enrolled will be based on the number of Relapses in the combined children and adolescent groups (age ≥ 6 to < 18 years of age). Subject enrollment will stop around the time that 49 Relapse events are anticipated to occur among these subjects. The number of Relapses among adults will not determine number of subjects enrolled in the study.

Assuming the proportions of child and adolescent subjects who Relapse in the R/WD period are 65% in the placebo group and 34% in the ecopipam group, approximately 98 subjects (~49 subjects per treatment group) may need to be Randomized to achieve this number of Relapse events.

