11.1. Primary Efficacy Assessment

The primary efficacy endpoint for this trial is the time from Randomization (Week 12) to Relapse, defined as the loss of $\geq 50\%$ of the improvement experienced in the YGTSS-TTS from Baseline (Day 1) to the last visit of the open-label Stabilization period (Week 12), or initiation of additional medications to treat symptoms of TD, or requirement of hospitalization for worsening symptoms of TD in subjects between the ages of $_6$ and <18 years for ecopipam compared to those receiving placebo during the double-blind, R/WD period.

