13.5. Sample Size Justifications

The planned number of Relapse events for the double-blind R/WD Phase is 49 children and adolescents. This number of events will provide 85% power to detect a difference between treatment groups, assuming a hazard ratio of 0.4 for Relapse and statistical testing at alpha level 0.05 (2-sided). Subject enrollment will stop around the time that 49 Relapse events among children and adolescents are expected to have occurred. The number of Relapses among adults will not determine study completion.

Assuming the proportion of subjects who Relapse in the DB randomization phase is 65% in the placebo group and 34% in the ecopipam group, approximately 98 subjects (49 subjects per group) will be required to achieve this number of events.

Total Number of Subjects:

Approximately 196 subjects (children and adolescents) will be enrolled into the open-label Stabilization Period in order to randomize 98 subjects age ≥ 6 to < 18 years of age assuming the stabilization rate in the open-label Stabilization Period is 50%. n addition, approximately 40 adult subjects are also expected to be enrolled.

Protocol EBS-101-TD-301 Version 9.0, 05 March 2024

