# 12.1. Adverse Events / Adverse Drug Reactions

An adverse event (AE) is any untoward medical condition that occurs in a patient while participating in this clinical study. Adverse events will be coded according to the Medical Dictionary for Regulatory Activities (MedDRA 25.0 or later) terminology and the severity of the toxicities will be graded according to the National Cancer Institute (NCI) Common Toxicity Criteria for Adverse Events (CTCAE), v4.03, where applicable. An adverse drug reaction (ADR) means any AE caused by a drug or biologic.

This document is confidential.

SAP text Version: SAP text 3.0 6-Dec-2023

Controlled Document ID: 3903A.02, Effective Date 31-Aug-2020

A Clinical Adjudication Committee (CAC) will review selected treatment emergent neurological adverse events that are known to occur as the result of dopamine receptor antagonists (see Appendix 16.5). The details of the CAC procedures and adjudication process will be reported in a CAC charter.

Treatment-Emergent Adverse Events (TEAEs) are those adverse events/adverse drug reactions that are recorded during or following the initiation of study treatment administration, and do not necessarily have a causal relationship to the use of the study medication. Treatment-Emergent Adverse Events (simply referred to as adverse events in summary tables) will be summarized.

The following adverse event summary tables will be summarized by treatment group:

- An overall summary with the number and percentage of patients reporting AEs, serious AEs
  (SAEs), maximum severity AEs, treatment-related AEs, treatment related SAEs, AEs leading to
  study treatment discontinuation and AEs with outcome of deaths.
- 2) AEs overall and by system organ class and preferred term.

In this summary, a patient is counted once at the system organ class and once at each preferred term within the system organ class.

- AEs overall and by system organ class, preferred term and initial daily dose level.
- 4) AEs overall and by system organ class, preferred term and region.
- 5) AEs overall and by system organ class, preferred term and weight band.
- 6) AEs overall and by system organ class, preferred term and time within the titration phase of open-label stabilization period. In all summaries by time the time windows are based on time since fist dose of ecopipam and will be as follows: 1-7, 8-14, 15-21, 22-28, 29-56, 57-84, 85-91, 92-98, 99-105, 106-112, 113-126, 127-140, 141-154, 155-168, 169-175, 176-184.

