- 7) AEs overall and by system organ class, preferred term and time within open-label stabilization period.
- 8) AEs overall and by system organ class, preferred term and time within the double-blind randomized withdrawal period.
- 9) AEs overall and by system organ class, preferred term and time within the safety follow up.
- 10) AEs overall and by system organ class, preferred term and maximum severity.

In this summary, a patient is counted once at the highest severity for which the event occurred in the system organ class and the highest severity for each unique preferred term within that system organ class. Therefore, patients may only contribute once to each preferred term and once to each system organ class.

11) Study-treatment-related AEs overall and by system organ class and preferred term.

All those AEs with relationship to treatment marked as "Possibly Related" or "Probably Related" or missing will be reported in the table.

- 12) Study-treatment related AEs by system organ class, preferred term and maximum severity
- 13) AEs leading to study treatment termination by system organ class and preferred term.
- 14) AEs leading to study treatment termination by system organ class, preferred term and maximum severity.
- 15) AEs by maximum severity, maximum relatedness and milestones (Up-titration, Open-label maintenance, double-blind R/WD (Weeks 13-16), double-blind R/WD (Weeks 17-24) and Down-titration).

A Serious Adverse Event (SAE) is an AE which falls into one or more of the following categories:

- Results in death.
- · It is immediately life-threatening.
- It requires in-subject hospitalization or prolongation of existing hospitalization.
- It results in persistent or significant disability or incapacity.
- Results in a congenital abnormality or birth defect.
- It is an important medical event that may jeopardize the subject or may require medical intervention to prevent one of the outcomes listed above.

Serious adverse events will be summarized by treatment group and combined over both treatment groups. A summary by age group (Children (≥ 6 and < 12 years of age), Adolescents (≥ 12 and < 18 years of age), and Adults (≥ 18 years of age)) will also be provided.

16) SAEs overall and by system organ class and preferred term.

In this summary, a patient is counted once at the system organ class and once at each preferred term within the system organ class.

- 17) Treatment related SAEs overall and by system organ class and preferred term.

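### Protocol 12.2.1.1 makes worsening of TD an adverse event and the SAP never separates it, so pooled AE lines for the withdrawal period are tilted towards ecopipam to whatever extent Relapses are recorded as AEs

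*Protocol*

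**What the plan says.** Protocol 12.2.1.1 defines an AE to include "the deterioration of a preexisting medical condition including worsening of TD". AEs from screening to 30 days after treatment stops, related or not, "must be recorded on forms provided by Sponsor or its representatives". The studied disease is therefore named in the AE definition.

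The primary endpoint, Relapse (Protocol 11.1), has three routes: losing at least half of the YGTSS-TTS improvement gained between Day 1 and Week 12, starting another medicine for TD, or "requirement of hospitalization for worsening symptoms of TD". Under Protocol 7.1 a subject who relapses stops blinded drug. Hospitalization is also a seriousness criterion in Protocol 12.2.1.2.

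The Synopsis plans for Relapse in "65% in the placebo group and 34% in the ecopipam group".

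SAP 12 summarizes R/WD AEs by treatment group, laid out so that the groups can be compared. SAP 12.1 lists the tables, among them an overall subject-level summary (table 1), "AEs overall and by system organ class and preferred term" (table 2), maximum severity (table 10), "AEs leading to study treatment termination by system organ class and preferred term" (table 13, with a severity version in table 14) and SAEs (table 16). Protocol 13.4.2 and SAP 8.2, 12 and 12.1 contain no exclusion, flag or separate tabulation for TD worsening or Relapse.

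**The concern.** Withdrawing drug in one arm is meant to bring tics back, so TD worsening should be more frequent on placebo if ecopipam works. Where those events are entered as AEs, a line such as the percentage of subjects with any AE becomes partly a second reading of efficacy, and it is tilted towards ecopipam.

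The R/WD period is the only randomized, placebo-controlled safety comparison in the trial, and safety is a secondary objective. SAP 2.2 also makes safety a main purpose of the interim review, so the monitoring board would see the same pooled lines.

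The preferred-term rows do not allow a reader to undo this. A subject with a tic AE may also have had another AE, so the tic row cannot be subtracted from the any-AE line to recover the number of subjects with a non-TD event.

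**Working it through.** **1. Check the planning figures.** Inputs from Protocol 13.5: hazard ratio 0.4, two-sided alpha 0.05, power 85%, Relapse 65% and 34%, 49 subjects per group.

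- Freedman events: (1.960 + 1.036)² × (1.4/0.6)² = 8.978 × 5.444 = 48.9, that is 49, as stated.
- Hazard ratio implied by the proportions: ln(0.66)/ln(0.35) = 0.396, consistent with 0.4.
- Expected Relapses: 49 × 0.65 = 31.85 on placebo and 49 × 0.34 = 16.66 on ecopipam, total 48.5.

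The Relapse proportions can therefore be used as the plan's own. If every Relapse were recorded, about 32 placebo and 17 ecopipam subjects would have an AE from Relapse alone, a gap of 65 - 34 = 31 points.

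**2. Effect on the any-AE line.** Let b be the non-TD AE incidence, r the Relapse proportion and f the share of Relapses recorded as AEs. If Relapse and other AEs are independent,

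P(any AE) = 1 - (1 - b)(1 - f·r).

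The documents give no R/WD AE rates, so b is an assumption. With b = 0.50 on ecopipam and 0.30 on placebo:

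- ecopipam: 0.50 + 0.50 × 0.34f = 0.50 + 0.170f
- placebo: 0.30 + 0.70 × 0.65f = 0.30 + 0.455f
- difference: 0.20 - 0.285f

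| f | Ecopipam | Placebo | Difference (points) |
|---|---|---|---|
| 0 | 50.0% | 30.0% | +20.0 |
| 0.25 | 54.3% | 41.4% | +12.9 |
| 0.50 | 58.5% | 52.8% | +5.8 |
| 0.70 | 61.9% | 61.9% | about 0 |
| 1 | 67.0% | 75.5% | -8.5 |

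The zero is at f = 0.20/0.285 = 0.70.

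**3. Other assumed rates.**

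- 50% vs 25%, the drug-related AE rates of the earlier crossover study PSY302 (Protocol 5.2.2), borrowed here only as an assumption: difference 0.25 - 0.3175f. This is +9.1 points at f = 0.5, -6.75 at f = 1, and zero at f = 0.79.
- Equal non-TD rates of 30%, f = 1: ecopipam 1 - 0.70 × 0.66 = 53.8%, placebo 75.5%. A gap of 21.7 points appears where none exists.
- Largest true ecopipam excess that would be fully hidden, for placebo non-TD rates of 25%, 40%, 50% and 60%: 35, 28, 23 and 19 points at f = 1; 14, 11, 9 and 7 points at f = 0.5.

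**4. Independence.** For the 50% vs 30% case at f = 1, complete overlap of Relapse and other AEs in both arms gives 50% vs 65% (-15 points). No overlap in either arm gives 84% vs 95% (-11 points). Opposite patterns in the two arms could give other values.

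**5. Which lines move.** Any AE, maximum severity, and the system organ class that holds the tic term are affected. So is any SAE, through TD hospitalization; the documents give no hospitalization rate, so that part cannot be sized. AEs leading to termination are affected only if the investigator marks the Relapse AE as the cause. Other preferred-term rows, the preferred-term table of AEs at 5% or more (table 19) and the special-interest tables (table 18) do not move.

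**The case against.** The strongest reply is that Relapse is not itself defined as an AE. It is a loss of improvement, and a subject scoring 30 at Day 1, 18 at Week 12 and 24 later has relapsed while still 6 points better than at Day 1. Protocol 12.2.1.1 gives no reference point for worsening. Protocol 12.4 has AEs arise from spontaneous reports, open questions or observation, and nothing tells sites to turn a YGTSS threshold into an AE. This stands. A reader might infer that a site following the protocol enters an AE for nearly every Relapse, but the documents do not support that. They leave the share open, and f = 1 is an upper bound.

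A reader might also infer that every Relapse enters the termination tables because Relapse ends blinded drug. The documents point the other way: Protocol 7.5 lists loss of efficacy separately from AEs as a reason for discontinuing, and SAP 10.2.2 treats an AE as a reason unrelated to Relapse. The route stays open only through the per-AE discontinuation field in Protocol 12.4.

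The assumed rates can also be challenged. Subjects in the R/WD period are responders who tolerated 12 weeks of drug, so a 20-point excess may not arise. The AE tables carry no planned tests, all data are listed, and treatment-related AEs have their own tables. These points limit the size and the consequences. They do not remove the direction of the bias in the pooled lines or make those lines recoverable from the preferred-term rows.

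**Conclusion.** The concern holds as a directional bias of unknown size in the pooled subject-level R/WD lines. It follows from a stated rule (worsening of TD is an AE and must be recorded) combined with the absence of any separation in the analysis plan. Under the planned Relapse proportions, with 50% vs 30% non-TD incidence and independence assumed, a true +20-point difference would be reported as about +13, +6 or -8.5 points when 25%, 50% or 100% of Relapses are recorded.

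That the AE comparison will be reversed is a stronger reading that the documents do not support. In this illustration it needs more than about 70% of Relapses to be recorded, and neither document fixes that share. With equal true rates, on the other hand, any recording makes ecopipam look safer.

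The Relapse proportions are paediatric planning values. Adults also enter the safety tables, and no adult Relapse rate is given.

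**What to change.** Leave Protocol 12.2.1.1 and SAE reporting as they are, and keep collecting and reporting all TD-worsening events. Recording TD worsening only when it is serious would be a mistake, because it would discard safety information during taper.

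In SAP 12.1, prespecify a list of preferred terms for worsening of TD or tics, to be fixed at the blinded data review. For the R/WD period, show the overall and pooled lines of tables 1, 2, 10, 13, 14 and 16 both with and without those terms, with TD worsening on its own line. Table 19 need not be rerun, because it is already by preferred term.

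The cost is a few sentences in the SAP, a short term list and a second version of a few R/WD summary lines. No data are lost.
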